10.1.2. Montelukast and Placebo

10.1.2.1. Administration

Montelukast (10 mg once daily in the evening) should be administered according to the prevailing product label (Singulair[®]). Randomized treatments (montelukast or placebo) will be administered only until Week 8 of the study.

CONFIDENTIAL

If a subject does not remember to take a dose within 8 hours of the scheduled time (i.e., at least 4 hours before the next scheduled dose), the dose should be skipped, and the next dose should be taken as scheduled. Doses should not be doubled-up, or a missed dose taken the next day, to make up for missed doses.

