2 STUDY OBJECTIVES AND ENDPOINTS

2.1 Primary Objective and Endpoint

The primary objective of this study is to evaluate whether Montelukast can reduce the severity of gastrointestinal (GI) events, measured by the Gastrointestinal Symptom Rating Scale (GSRS), after oral administration of Dimethyl Fumarate (DMF) in subjects with relapsing forms of multiple sclerosis (MS).

The primary endpoint of this study is the proportion of subjects with a worsening in the severity of GI adverse events (AEs), measured by the average change from Day 0 to Day 10 in GSRS score. If a patient takes the randomized study treatment one day after his or her GSRS score reaches the GI threshold, Day 0 is defined as the day prior to the first dose of randomized study treatment. If a patient takes the randomized study treatment on the same day when the GSRS score reaches the GI threshold, Day 0 is defined as the day with the first dose of randomized study treatment. If a patient missed the randomized study treatment for a few days after the GSRS score reached the GI threshold, Day 0 is the day immediately prior to the first dose when the GI threshold was reached. Day 10 is defined as 10 days after Day 0.

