2.2 Secondary Objectives and Endpoints

[figure not shown]
The secondary objectives in this study population are:

- To evaluate whether Montelukast after oral administration of DMF in subjects with relapsing forms of MS:
 - decreases discontinuations due to GI events
 - reduces the number of subjects taking symptomatic therapies for GI events
- To investigate the effect of Montelukast on the incidence of flushing events after oral administration of 240 mg DMF in subjects with relapsing forms of MS

The secondary endpoints are:

- Average change of GI severity scores from Day 0 to Day 10, as measured by the total change of GSRS scores from Day 0 over the first 10 days (Day 1 to Day 10), divided by the total number of days with GSRS recorded
- Average change of GI severity scores from Day 0 to Week 10, as measured by the total change of GSRS score from Day 0 over the first 10 weeks (Day 1 to Week 10), divided by the total number of days with GSRS recorded

- Time to first worsening of GSRS in GI severity
- Time to recovery to Day 0 GSRS score from the last occurrence of the worst score in GI severity
- Average change of GSRS score from Day 0 score to Weeks 1, 2, 3, 4, 5, 6, and 8
- Average change of GSRS score from Day 0 to 72 hours from the initiation of randomized study treatment
- Proportion of subjects who require GI symptomatic therapy during the study
- Percentage of subjects who discontinue DMF therapy due to GI-related AEs from Day 0 to Week 10
- Proportion of subjects who experience flushing events

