Average change of GSRS score from baseline (Day 0) to Week 1, 2, 3, 4, 5, 6 and 8 will be summarized; a repeated measures model for the change of the GSRS score from baseline, adjusted for age, weight and baseline GSRS score, will be used to estimate effect at each time point. Sensitivity analyses using ANCOVA model for the average change may be performed.

Average change of GSRS score from Day 0 to 72 hours from the initiation of randomized study treatment

Average change of GSRS score from baseline (Day 0) to 72 hours (Day 3) from the initiation of randomized study treatment will be summarized and analyzed by the repeated measures method. No sensitivity analysis will be performed.

Proportion of subjects who take GI symptomatic therapy during the study

From Day 10 onward, subjects are allowed to use symptomatic therapy to treat DMFrelated GI events. The proportion of subjects who take GI symptomatic therapy from Day 10 to Week 10 will be summarized by treatment and analyzed using the Chi-squared test.

[figure not shown]
Percentage of subjects who discontinue DMF therapy due to the GI-related adverse events from Day 0 to Week 10

The proportion of subjects who discontinue DMF due to the GI-related adverse events from Day 0 to Week 10 will be summarized by treatment and analyzed using the Chi-squared test.

Proportion of subjects who experience flushing events

The proportion of subjects who experience flushing events from Day 0 to Week 10 will be summarized for the modified ITT population by treatment group and analyzed using the Chi-squared test. Flushing event as defined as an event coded to any of the following preferred terms: Flushing, Hot flush (under SOC of Vascular disorders), Erythema, Generalized erythema, Skin burning sensation (under SOC of Skin and subcutaneous tissue disorders), Burning sensation (under SOC of Nervous system disorders), Feeling hot (under SOC of General disorders and Administration site conditions), Hyperaemia (under SOC of Vascular disorders).

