Table 21: Summary of average change of GSRS score from baseline (Day 0) by repeated measures analysis, Day 1 to Weeks 1-8

Table 22: Summary of average change of GSRS score from baseline (Day 0) by repeated measures analysis, at 72 hours from the initiation of randomized study treatment (Day 1 - Day 3)

Table 23: Summary of primary endpoint by baseline demographic and disease characteristics

Table 24: Summary of average change of GI severity score from baseline (Day 0), repeated measures analysis, Day 1 to Day 10, by baseline demographic and disease characteristics

Table 25: Summary of average change of GI severity score from baseline (Day 0), repeated measures analysis, Day 1 to Week 10, by baseline demographic and disease characteristics

Table 26: Summary of proportion of subjects who take GI symptomatic therapy during the study

Table 27: Summary of proportion of subjects who discontinue DMF therapy due to GI-related adverse events from Day 0 to Week 10

Table 28: Summary of proportion of subjects who experience flushing events

Table 29: Summary of biomarker scores, changes and percent changes from Tecfidera baseline, by treatment group and visit, DMF safety analysis population

Table 30: Summary of biomarker scores, changes and percent changes from Montelukast baseline, by treatment group and visit, Montelukast/placebo safety analysis population

Table 31.1: Summary of selected hematology parameters, change and percent change from Montelukast baseline, by treatment group and visit, Montelukast/placebo safety analysis population

Table 31.2: Summary of selected hematology parameters, change and percent change from Tecfidera baseline, by treatment group and visit, DMF safety analysis population

Table 32.1: Summary of hematology abnormalities by CTC grades, by treatment group and visit, DMF safety analysis population

Table 32.2: Summary of hematology abnormalities by CTC grades, by treatment group and visit, Montelukast /placebo safety analysis population

Table 33.1: Incidence of adverse events by system organ class and preferred term, Montelukast/placebo safety analysis population

Table 33.2: Incidence of adverse events by system organ class and preferred term, DMF safety analysis population

Table 34.1: Incidence of serious adverse events by system organ class and preferred term, Montelukast/placebo safety analysis population

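### The SAP labels Day 3 as 72 hours after starting randomized treatment for every subject, but for next-day starters Day 3 is nominally 48 hours

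*Combined protocol and SAP*

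**What the plan says.** The endpoint in SAP 2.2 is "Average change of GSRS score from Day 0 to 72 hours from the initiation of randomized study treatment". SAP 7.3.4 turns this into a study day: "Average change of GSRS score from baseline (Day 0) to 72 hours (Day 3) from the initiation of randomized study treatment will be summarized". It plans a repeated measures analysis with no sensitivity analysis. The title of Table 22 in SAP section 8 describes the output as "at 72 hours from the initiation of randomized study treatment (Day 1 - Day 3".

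Study days are counted from Day 0, and SAP 2.1 gives three rules for it:

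- Dose taken one day after the threshold is reached: "Day 0 is defined as the day prior to the first dose of randomized study treatment".
- Dose taken on the threshold day: "Day 0 is defined as the day with the first dose of randomized study treatment".
- Dose missed for a few days after the threshold: "Day 0 is the day immediately prior to the first dose when the GI threshold was reached".

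Protocol 10.1.2.1 sets the time of day: "Montelukast (10 mg once daily in the evening) should be administered according to the prevailing product label". Protocol 7.2.4 has the eDiary alert tell subjects to start on the day of the alert. Protocol 4.4 makes the GSRS a daily-recall score. The documents do not give the clock time of the diary entry.

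**The concern.** The endpoint is timed from first dose but located by days since Day 0. Those two origins coincide for some subjects and differ by a day or more for others, and nothing in SAP 7.3.4 or Table 22 adjusts for which Day 0 rule applied. A result headed 72 hours would therefore pool subjects at different times since first dose. If the estimate is an average over Days 1 to 3, it would also count a mostly untreated day as treated for some of them. This is the only endpoint expressed in hours from first dose, and no sensitivity analysis for it would reveal the mismatch.

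**Working it through.** **Inputs.** Day k is k days after Day 0 (SAP 2.1 defines Day 10 in this way). Let f be the study day of the first randomized dose. From SAP 2.1, f = 0 for same-day starters and f = 1 for next-day starters. Dosing is once daily in the evening (protocol 10.1.2.1). I assume that evening means 17:00 to 22:00; the documents give no clock time.

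**Formula.** Hours since first dose, at the same clock time on Day 3 = 24 × (3 − f).

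**Same-day starters (f = 0).** 24 × 3 = 72 hours, after three earlier doses (Days 0, 1 and 2). The SAP's figure is reproduced. Calendar Day 3 runs from 55 to 79 hours after a 17:00 first dose and from 50 to 74 hours after a 22:00 first dose, so it contains the 72-hour point.

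**Next-day starters (f = 1).** 24 × 2 = 48 hours, after two earlier doses (Days 1 and 2).

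- Calendar Day 3 runs from 31 to 55 hours after a 17:00 first dose and from 26 to 50 hours after a 22:00 first dose. No point on Day 3 reaches 72 hours, whatever the time of the diary entry.
- The 72-hour point is on Day 4: 24 × (4 − 1) = 72.
- On Day 1, 17 to 22 of 24 hours (71% to 92%) come before the first dose.

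**Later starters.** The third rule in SAP 2.1 can be read in two ways.

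- Day 0 is the day before the first dose: f = 1, so Day 3 is again 48 hours.
- Day 0 is the threshold day and the first dose comes k days later: f = k, so Day 3 is 72 − 24k hours. That is 24 hours at k = 2 and 0 hours at k = 3.

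**Size across the sample.** Let q be the share of subjects with f = 1. The documents do not give q.

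- Mean nominal time at Day 3 = 72 − 24q: 66 hours at q = 0.25 and 60 hours at q = 0.50.
- If Days 1 to 3 are averaged, with no treatment effect on Day 1 for these subjects and an equal effect on all other days, one of their three days contributes nothing. The average effect falls by q/3: 0.25/3 = 8% and 0.50/3 = 17%.
- If the estimate is taken at Day 3 alone, the Day 1 dilution does not arise. What remains is the mix of 48 and 72 hours, which changes the estimate only if the effect is still developing between those times.

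**The case against.** The strongest reply is that the mapping is right for the path the protocol prescribes. Subjects are told to start on the day of the alert; SAP 2.1 makes that day Day 0, and Day 3 is then 72 hours. Those who start later depart from the instruction and may be few. This stands as a limit on reach. It does not make the rule correct for the others, because SAP 2.1 writes separate provisions for them.

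A second reply is that a daily-recall score with no stated entry time cannot support hour-level precision, and that Days 1 to 3 are a next-day starter's first three dosing days. The lack of precision is real, but no hour of that subject's Day 3 is as late as 72 hours. A window defined as the first three dosing days would also need a different label.

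Third, day-by-day change over Days 1 to 10 is already planned (Table P1, Figures 1 and 2), so the early course, including Day 4, will be visible. That lowers the stakes, but those displays use the same Day 0 numbering.

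A reader might also infer more than the documents support:

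- That Day 3 is 48 hours for everyone. This joins the protocol's single Day 0 (the day before first dose, protocol 6.2.1) to a Day 3 label found only in the SAP. The protocol never assigns the 72-hour endpoint to a study day.
- That the effect is diluted by up to 33%. That figure requires every subject to start late and Days 1 to 3 to be averaged. SAP 7.3.4 can be read as an estimate at Day 3; only the title of Table 22 points to an average.
- That the comparison between arms is biased. Both arms follow the same rule under blinding.
- That this endpoint is the formal test of the 81% fall within 72 hours cited in protocol 5.2. The protocol gives that result as background and does not link it to this endpoint.

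**Conclusion.** The point holds for subjects whose first dose does not fall on Day 0. For next-day starters the stated time point is wrong by a nominal 24 hours. For later starters it is wrong by 24 hours or more, depending on how an ambiguous rule is read. For same-day starters it is correct.

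The consequence is a mislabelled time point and possible dilution of one secondary endpoint. The size cannot be fixed from the documents, because the share of affected subjects is not given. The 8% and 17% figures are illustrations that rest on assumed shares, an average over Days 1 to 3, no effect on Day 1, and an equal effect on the other days. The timing arithmetic is certain; the practical impact is not. The change is worth making because the rule gives a wrong time point for a group the SAP itself provides for, and correcting it is cheap.

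**What to change.** Define this endpoint from the recorded date of the first randomized dose, with the Day 0 score as baseline. The 72-hour point is first-dose date + 3 days; if an average is intended, the window is first-dose date + 1 to + 3. Replace the Day 3 label in SAP 7.3.4 and the Day 1 to Day 3 range in the title of Table 22 to match, and make the two agree on whether the estimate is at that day or averaged to it. Same-day starters are unchanged. Next-day starters move to Day 4, or to Days 2 to 4.

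The cost is one derivation and two wording changes. No new data are needed: the eDiary records randomized dosing, and SAP 7.2.7 already uses the first-dose date for exposure. The downside is that study-day numbers for this endpoint will differ between subjects and from the other GSRS analyses, which a footnote to Table 22 should state. Re-anchoring settles the timing for late starters but not their baseline, so the third Day 0 rule in SAP 2.1 still needs one unambiguous reading.

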16.4.4. Secondary Endpoints Analysis

The average change of GI severity score from Day 0 to Week 10 will be analyzed using an analysis of covariance (ANCOVA) model to adjust for covariates and confounding factors such as early drop-outs. Time to first worsening and time to recovery from the last worst GSRS score to Day 0 GSRS score will be analyzed using Kaplan-Meier methods and a Cox proportional

CONFIDENTIAL

hazards model. The average change of GSRS score from Day 0 score at various timepoints will be analyzed using an ANCOVA model adjusting for covariates and confounding factors.

The proportion of subjects who require GI symptomatic therapy during the study period will be compared using the chi-square test. The percentage of subjects who discontinue DMF therapy due to GI-related events from the Randomization Visit to Week 10 will be summarized by treatment arm. The proportion of subjects who experience flushing events in each treatment group will also be summarized.

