7 STATISTICAL ANALYSIS METHODS

The statistical software, SAS[®], will be used for all summaries and statistical analyses.

Summary statistics will be used throughout. For continuous endpoints, the summary statistics will generally include: the number of subjects with data, mean, standard deviation (SD), median, 25th and 75th percentile (Q1, Q3), minimum and maximum. For categorical endpoints, the summary statistics will generally include: number of patients randomized and dosed, the number of patients with data, and the number and percent of subjects with data in each category.

All statistical tests will be 2-sided with a type I error rate of 5%, unless otherwise specified.

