7.1 Analysis of baseline data

Baseline GSRS score is defined as the score collected at Day 0.

Baseline data of demographics and disease characteristics are defined as data collected at the Screening visit. If there is more than one value on or before the screening visit, the Baseline value will be selected from all measurements collected before or on the date of the screening visit; the value closest to the date of screening visit will be used as the Baseline value.

Definition of baseline value for clinical laboratory data

Tecfidera baseline value

The Tecfidera baseline value is defined as the measurement collected before or on the date of the Randomization visit. If there is more than one value on or before the Randomization visit date, then the Tecfidera baseline value will be selected from all measurements collected before or on the date of the Randomization visit; the value closest to the date of Randomization visit will be used as the Tecfidera baseline value.

Montelukast baseline value

The Montelukast baseline value is defined as the measurement collected before or on the date of first dose of Montelukast /placebo. If there is more than one value on or before the first dose date of Montelukast /placebo, then the Montelukast baseline value will be selected from all measurements collected prior to or on the date of the first dose of Montelukast/placebo; the value closest to the date of the first dose date will be used as the Montelukast baseline value.

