7.3.3 Analysis Methods-Primary endpoints

Proportion of subjects with a worsening in the severity of GI AEs, measured by the average change from Day 0 to Day 10 in GSRS score

The average change of the GSRS score from Day 0 (baseline) to Day 10 will be calculated as the sum of changes from baseline in GSRS score over the first 10 days divided by the total number of days with GSRS recorded. A positive average change of GSRS score from Day 0 to Day 10 means a patient has an overall worsened GI severity. A negative average change of GSRS score from Day 0 to Day 10 means an overall improved GI severity.

The proportion of subjects with worsening will be summarized by treatment and will be estimated from a weighted logistic regression model adjusted for age, weight and baseline GSRS score as continuous variables. Each patient included in this model will be assigned a weight defined as the proportion of days with GSRS score recorded. The weight is used to account for the missing data when patients do not report the GSRS score. The odds ratio (OR) for the Montelukast treatment group compared to placebo will be reported. The corresponding P-value from the likelihood ratio test of the null hypothesis that the OR = 1 will be given. Profile likelihood 95% profile likelihood confidence interval (CIs) will be given for the odds ratio.

SAS procedure "genmod" or SAS procedure "logistic" will be used to perform the primary analysis. Below is the example of SAS procedure genmod:

```
proc genmod data=ds1 descending;*assuming ds1 is the name of the data
set
    class trtpn;
    model worsec = trtpn weight age gsrsb/dist=bin link=logit lrci;
    weight pdays;
    lsmeans trtpn / pdiff cl;
    contrast "difference between treatments" trtpn -1 1;
run;
```

Depending on the GSRS, study treatment and/or the DMF compliance, sensitivity analysis may be performed among patients with a compliance rate from Day 0 to Day 10 above a certain threshold. A chi-squared test for the difference in the rate of worsening between the two treatment groups may also be performed.

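### Use of GI symptomatic therapy, a secondary objective, is compared without Day 0 GSRS as a covariate, which gives up a modest amount of precision

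*Combined protocol and SAP*

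**What the plan says.** SAP 2.2 lists among the secondary objectives whether montelukast "reduces the number of subjects taking symptomatic therapies for GI events". For the matching endpoint, SAP 7.3.4 says that the share of patients who "take GI symptomatic therapy from Day 10 to Week 10 will be summarized by treatment and analyzed using the Chi-squared test". Protocol 16.4.4 says: "The proportion of subjects who require GI symptomatic therapy during the study period will be compared using the chi-square test". Neither text names a covariate. The only output listed is "Table 26: Summary of proportion of subjects who take GI symptomatic therapy during the study"; no adjusted or sensitivity version is planned.

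Elsewhere the SAP adjusts. SAP 7.1 (baseline data) states: "Baseline GSRS score is defined as the score collected at Day 0". The binary primary endpoint is analysed in SAP 7.3.3 by a "weighted logistic regression model adjusted for age, weight and baseline GSRS score as continuous variables". In SAP 7.3.4 the same three covariates enter the Day 10 ANCOVA and MMRM, the Cox model for time to first worsening and the weekly repeated-measures model. The other two binary secondary endpoints, DMF discontinuation for GI events and flushing, also have only a chi-squared test.

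**The concern.** Symptom severity at the start of randomized treatment is a natural predictor of who later takes an anti-diarrhoeal, antacid or antiemetic. A prognostic baseline score that is left out of the comparison stays in the error variance. The plan accepts this reasoning for its primary binary endpoint and gives no reason for dropping it here.

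Precision is scarce. SAP 5 closes enrollment at about 60 dosed patients, against 118 planned. Day 0 severity arises only after randomization, when a subject on DMF reaches the symptom threshold, so the analysis is the only place where it can be taken into account. A wider interval and less power on a stated objective are at stake. SAP 7.3.4 also specifies only a summary and a test for this endpoint, with no effect estimate and interval.

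**Working it through.** **Inputs from the documents**
- Significance level (SAP 7): "All statistical tests will be 2-sided with a type I error rate of 5%, unless otherwise specified".
- Dosed fraction (protocol 7.1): 118/295 = 0.40.
- Sample size: 59 per arm planned (SAP 6); about 60 dosed at closure (SAP 5), so about 30 per arm at 1:1.
- Therapy use in earlier DMF studies (protocol 5.2): 11% to 16% of subjects, not selected for GI symptoms.

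**The plan's own sample size.** No power is stated for this endpoint. The primary endpoint's sample size (SAP 6) assumes 40% improving on placebo and a 30-point difference.
- n = [1.96·√(2·0.55·0.45) + 0.84·√(0.4·0.6 + 0.7·0.3)]² / 0.30² = 42 per arm.
- Continuity-corrected: 49 per arm. With 15% discontinuation: 49/0.85 = 57.6, so 58 per arm and 116 in total, against 118 stated. The figure reproduces.

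**Assumptions needed.** If every user in the earlier studies would have reached this trial's trigger, use among dosed subjects would be 11/0.40 = 27.5% to 16/0.40 = 40%. I take 40% v 20% as the main case and 16% v 5% as a low case. The odds ratio (OR) for use per SD of Day 0 GSRS is varied from 1 to 3.

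**Simulation.** Therapy use follows a logistic model on treatment and standardised Day 0 GSRS, with 6000 trials per cell and Monte Carlo error of about 0.6 points. The Pearson chi-squared test is compared with a likelihood-ratio test adjusted for Day 0 GSRS. The variance ratio is that of the standardised risk difference to the raw one.

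| Use; n per arm | Chi-squared power | Adjusted power at OR 1 / 1.5 / 2 / 3 | Variance ratio at OR 1 / 1.5 / 2 / 3 |
|---|---|---|---|
| 40% v 20%; 30 | about 39% | 41.5 / 42 / 44 / 48% | 1.02 / 1.00 / 0.95 / 0.85 |
| 40% v 20%; 59 | about 67% | 67 / 67 / 72 / 76% | 1.01 / 0.97 / 0.92 / 0.85 |
| 16% v 5%; 30 | about 30% | 34 / 34 / 36 / 37% | 1.02 / 1.01 / 0.98 / 0.93 |

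A further set of runs at 40% v 20% gave reductions of 8-9% at OR 2 and 16-18% at OR 3. Together the range is about 5-9% and 15-18%.

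**Separating the covariate from the change of test.** At 30 per arm the likelihood-ratio test rejects more often than Pearson even when the score predicts nothing, so the columns above overstate the covariate's share of the power gain. With 40% v 20% and a correlation of 0.3 (about OR 2), power was 38.9% for Pearson, 42.2% for the unadjusted likelihood-ratio test and 43.9% for the adjusted one. The covariate adds 43.9 − 42.2 = 1.7 points. At OR 3 it adds about 48 − 42 = 6. At a correlation of 0.15 it adds 40.9 − 40.7 = 0.2.

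**What this means for the interval.** At 30 per arm the raw risk difference has SE √(0.4·0.6/30 + 0.2·0.8/30) = 0.115, a 95% half-width of 22.6 points. Multiplying by √0.95 to √0.91 gives 22.1 to 21.6 points (OR 2). Multiplying by √0.85 to √0.82 gives 20.9 to 20.5 (OR 3). In patients, 60/0.95 to 60/0.91 is 63 to 66, and 60/0.85 to 60/0.82 is 71 to 73. The gain is worth roughly 3 to 6 or 11 to 13 extra patients. A 2% loss costs about one (60/1.02 = 59).

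**Type I error.** The chi-squared test rejected 4.0-5.2% of the time under the null at 40% use. The likelihood-ratio test with Day 0 GSRS alone runs at about 5-6% at 30 per arm. With age and weight added it ran at 5.9-6.7% at 40% use and 6.1-7.7% at 16%.

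**The case against.** The chi-squared test is simple, valid under 1:1 randomization and the same in both documents, and the SAP uses it for all three binary secondary endpoints. Day 0 GSRS is one day's score, taken at or near the trigger, while use is counted from Day 10 to Week 10 (10 to 70 days later), so it may predict weakly. With about 30 per arm the comparison is underpowered under either analysis. All of this stands, and it keeps the point small. The trigger does not make the covariate nearly constant, however. It acts on one item, whereas the overall score is the mean of 15 items: one item at 3 forces a mean of only 3/15 = 0.2 on a 0-6 scale. SAP 3.1 also records two different triggers across protocol versions.

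A reader might infer more than the documents support:
- **That a chance imbalance in Day 0 severity makes the planned test misleading.** At 30 per arm the difference in mean score has SE √(2/30) = 0.26 SD, so imbalances will occur. But the 5% level already allows for them, and the simulated error rate confirms it.
- **That randomization should have been stratified by severity.** Subjects are randomized before starting DMF, so Day 0 severity does not exist at that point.
- **That adjustment would gain 11 to 12 points of power.** That needs a correlation of 0.5, an odds ratio of about 4 per SD. Nothing in the documents supports this strength, and at 30 per arm part of the difference comes from the likelihood-ratio test.
- **That the primary model's full covariate set should be copied.** At 40% v 20%, only 30·0.40 + 30·0.20 = 18 users are expected, and the type I error drifts upward.

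**Conclusion.** The point holds as an inexpensive improvement to a secondary analysis, not as the correction of an error. The plan leaves out a baseline score that it already collects and uses in most of its other efficacy models. Under 40% v 20% use, this gives up about 5-9% of the variance of the risk difference at an odds ratio of 2 per SD and 15-18% at 3. The covariate itself is worth about 2 to 6 points of power at 30 per arm.

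The size rests on two assumptions that the documents cannot settle: the use rate and the prognostic strength. The 40% rate is the top of the derived range. At 16% v 5% the variance reduction is only about 2-7%. If the score predicts nothing, at most about 2% is lost. The balance favours adjustment, but it would not rescue an underpowered comparison.

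**What to change.** In SAP 7.3.4, before any group-level results are reviewed:
- Pre-specify a logistic regression of GI symptomatic therapy use on treatment, with Day 0 GSRS (the SAP's baseline score) as the only covariate. Omit age and weight, given about 60 dosed patients and few expected users.
- Report the standardised risk difference (predicted risks averaged over all analysed patients under each treatment) with its 95% CI. An adjusted odds ratio alone will not do: it is a conditional measure, and its standard error need not shrink.
- Keep the chi-squared test alongside, so that the SAP stays in line with protocol 16.4.4, and name it as the fallback if users are very few. State the cut-off number in advance.
- Add the adjusted result to Table 26.

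The cost is a few sentences in the SAP and a few lines of code, on data already collected. The small downside is reliance on a model, with a likelihood-ratio type I error of about 5-6% at 30 per arm.
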